9.1.1 UI Survey

A survey, written in Italian by the authors, will collect women's socio-demographic, economic and clinical characteristics, based on the variables reported in Table 1. The entire survey is attached in Appendix.

 
I.R.C.C.S. Ospedale San Raffaele
	
STUDY PROTOCOL
	
WUIPS Version n. 1 23.08.2023

---	------------------------------	---

A total of 29 questions will attempt to acquire information about some of the previously defined variables: specifically, 23 questions will be related to socio-demographic and clinical predictors of UI (n. 1-23), one question will be about the onset of the UI symptomatology (n. 35), one question about sexuality (n. 36) and four questions will investigate the direct and indirect costs of UI (n. 37-40). The survey was tested as a pilot on a sample of 13 women aged between 40 and 65 years old and was assessed as suitable for the following aspects: understanding and clarity of the questions, absence of questions that put the participant in difficulty, completion time (which resulted maximum of 5 minutes).

9.1.2 International Consultation of Incontinence Modular Questionnaire Urinary Incontinence Short Form (ICIQ UI-SF)

The International Consultation of Incontinence Modular Questionnaire Urinary Incontinence Short Form (ICIQ UI-SF) is a questionnaire that allows the assessment of the prevalence, frequency, and perceived cause of UI and its impact on everyday life. It is an appropriate scale for estimating national prevalence in representative samples (Bedretdinova et al., 2015).

ICIQ UI-SF was developed and validated in English for the first time by Avery and colleagues in 2004, and then Tubaro and colleagues made an Italian Validation in 2006. This last version will be used in the study.

The questionnaire comprises four question items and the reference period for symptom assessment is the four weeks preceding the day that the questionnaire is administered. The total score for the ICIQ-SF is calculated as the sum of scores obtained from the frequency of urinary incontinence episodes (from 0 or 'never', increasing by 1 unit up to 5 or 'always'), perceived quantity of urine losses (0 or 'no loss', increasing by 2 units up to 6 or 'a large amount') and quality of life (from 0 or 'no interference' of urinary incontinence with life, increasing by 1 unit up to 10 or 'maximum interference'). The theoretical range of total score values is therefore 0-21. A higher score indicates greater impairment from incontinence. The fourth question is an unscored self-diagnostic item about the type of urine leakage (Tubaro et al., 2006).

The instrument has a GRADE A on the level of validation according to the International Consultation of Incontinence (ICI) grades of recommendation; this means that the questionnaire has good validity, reliability and responsiveness established with rigor in several data sets. Specifically, the internal consistency of the ICIQ-SF is satisfactory overall, with a Cronbach's α of 0.896. Also the test-retest reliability is good; the Pearson r coefficient is almost equal to 1 for the total score and varies steadily at ≈ 0.9 for all items. Intraclass correlation coefficients for the total score and the quality of life item are, respectively, 0.93 and 0.96 (Tubaro et al., 2006). The entire questionnaire is attached in the Appendix (questions n. 24-27).

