4. OUTCOMES

Primary outcome

- Prevalence of middle-aged women with urinary incontinence.

Secondary outcomes

- Description of UI and related predictors, quality of life, social impact and costs.
- Association between UI and related predictors, quality of life, social impact and costs.

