UI prevalence and symptomatology	Lifestyle factors	
 Unhealthy voiding behavior (Hu and Pierre, 2019) and low physical activity may contribute to UUI onset (Li et al., 2023) Smoking cessation is a general public health measure and has been shown to be weakly associated with improving urgency, frequency and UI (Danforth et al., 2006; Harding et al., 2023) Decrease in fluid intake may improve some symptoms in patients with SUI and idiopathic detrusor overactivity (Swithinbank et al., 2005) Reduction of caffeine intake may reduce symptoms of frequency and urgency (Harding et al., 2023) An association was seen between alcohol consumption and urinary incontinence in middle-aged and older women (Lee & Hirayama, 2012)
	Frequency of urine leakage	To assess the severity of UI among female, we need measuring the “frequency” and “usual amount” of leakage ranged from “moderate” to “strong” (Avery et al., 2004)
	Perceived quantity of urine leakage	
	Type of urine leakage	It is focused on subtypes of urinary incontinence (SUI, UUI and MUI) (Abrams et al., 2003)
	Time of onset of urine leakage	The mean age in which urine leakage begins seems to be lower for SUI compared to MUI and UUI (Thangarajah et al., 2020)

 
I.R.C.C.S. Ospedale San Raffaele
	
STUDY PROTOCOL
	
WUIPS Version n. 1 23.08.2023

---	------------------------------	---

UI quality of life, social impact	General interference with daily life	The measurement of UI should incorporate the impact that the condition may have on quality of life (Avery et al., 2004)
	Interference with specifical activities	
Specifically:
 
 • Physical Activity • Social Relationships • Travel • Emotional Health 
(Monticone et al., 2021; Shumaker et al., 1994)

	Interference with sexual life	Some articles report that UI affects sexual aspects of the individual (Felsted & Supiano, 2019; Marques et al., 2015). According to other studies, sexual activity does not seem to be damaged by UI (Siracusano et al., 2003)
Costs	Work productivity	UI imposes a high economic burden because of work productivity loss (Goren et al., 2014)
	Weekly costs of hygiene care products	UI is associated with substantial routine care “costs” (Subak et al., 2006)

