- 5. Ho perdite di urina quando sono in movimento e durante l'attività fisica
- 6. Ho perdite di urina quando ho finito di urinare e mi sono rivestita
- 7. Ho perdite di urina senza ragioni particolari
- 8. Ho perdite di urina continuamente

Incontinence Impact Questionnaire-7 (Italian)

Le saremmo grati se rispondesse a queste ultime domande, per comprendere l'influenza sulla qualità di vita delle perdite di urina che ha riscontrato.

NOTA BENE: Se non ha mai riscontrato perdite di urina, le chiediamo di apporre una crocetta sul seguente quadratino e di non rispondere alle domande nella tabella. Grazie per la collaborazione.

- Non ho perdite di urina

Se ha riscontrato perdite di urine, queste perdite hanno influenzato...

	Per nulla	Molto poco	Un po'	Molto
28. La sua capacità di fare le faccende domestiche (cucina, pulizie di casa, lavanderia, ecc.)?	0	1	2	3
29. Le sue attività fisiche ricreative, come camminare, nuotare, o fare	0	1	2	3

altro esercizio?				
30. Le sue attività del tempo libero (andare al cinema, concerti, ecc.)?	0	1	2	3
31. La sua capacità di viaggiare in auto o in autobus per più di 30 minuti da casa?	0	1	2	3
32. La sua partecipazione ad attività sociali fuori casa?	0	1	2	3
33. La sua salute emotiva (nervosismo, depressione, ecc.)?	0	1	2	3
34. I suoi sentimenti di frustrazione?	0	1	2	3

Di seguito le poniamo qualche domanda su insorgenza, evoluzione, impatto della patologia e costi da essa derivanti.

NOTA BENE: Se non ha mai riscontrato perdite di urina, le chiediamo di apporre una crocetta sul seguente quadratino e di non rispondere alle domande successive. Grazie per la collaborazione.

Non ho perdite di urina

35. Da quanto tempo ha delle perdite di urina?

- 1. Da 1 anno o meno
- 2. Da 2-5 anni
- 3. Da 6-10 anni
- 4. Da più di 10 anni

36. Le sue perdite di urina hanno influenzato la sua vita sessuale?

- 1. Per nulla
- 2. Molto poco
- 3. Un po'
- 4. Molto

37. Le sue perdite di urina hanno comportato assenteismo o minore produttività sul posto di lavoro?

- 1. No
- 2. Sì, raramente
- 3. Sì, a volte
- 4. Sì, spesso

38. In media, potrebbe fornire una stima della spesa settimanale che sostiene per l'acquisto di prodotti igienici specifici per le perdite di urina (assorbenti o pannolini, salviettine, detergenti intimi specifici, ecc.)?

- 1. Non acquisto alcun prodotto specifico per le perdite di urina
- 2. Spendono meno di 3 euro a settimana
- 3. Spendono fino a 5 euro a settimana

- 4. Spendò tra i 6 e i 10 euro a settimana

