- 5. Spendò più di 10 euro a settimana

39. Ha svolto delle visite specialistiche per il problema delle perdite di urina?

- 1. No (perché _____)
- 2. Sì, con un ginecologo / un urologo
- 3. Sì, con un'ostetrica / un infermiere / un fisioterapista
- 4. Sì, con un altro professionista sanitario (specificare _____)

40. Sta seguendo qualche trattamento per risolvere il problema delle perdite di urina?

- 1. Sì (specificare _____)
- 2. No

LA RINGRAZIAMO MOLTO PER AVER RISPOSTO ALLE NOSTRE DOMANDE

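### Only question 38 yields a monetary value: questions 37, 39 and 40 record no count or amount, so no indirect, healthcare or total cost per woman can be estimated

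*Protocol*

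**What the plan says.** Section 4 of the protocol names costs in both secondary outcomes: "Description of UI and related predictors, quality of life, social impact and costs", and "Association between UI and related predictors, quality of life, social impact and costs". Section 5(d) expects to describe the costs of women with urinary incontinence (UI).

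Table 1 in section 9 has three rows under Costs: work productivity, weekly costs of hygiene products, and healthcare resource utilization (specialist visits and treatments). The stated reason for the first is economic: "UI imposes a high economic burden because of work productivity loss". The reason for the third is higher resource use and higher costs to payers.

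Section 9.1.1 assigns four items of the researcher-written survey to this domain: "four questions will investigate the direct and indirect costs of UI (n. 37-40").

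Three of the four items in the appendix read:

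- "37. Le sue perdite di urina hanno comportato assenteismo o minore produttività sul posto di lavoro" (no; yes, rarely; yes, sometimes; yes, often).
- "39. Ha svolto delle visite specialistiche per il problema delle perdite di urina" (no, with reason; or yes, by type of professional).
- "40. Sta seguendo qualche trattamento per risolvere il problema delle perdite di urina" (yes, specify; or no).

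Question 38, the other one, asks for weekly spend on hygiene products in five euro bands.

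**The concern.** A cost needs either an amount of money, or a quantity that can be multiplied by a unit value, and in both cases a period. Three of the four items supply neither an amount nor a quantity. This is true even for a working woman who answers every item fully and accurately.

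Indirect cost is the weakest part, because question 37 is its only source. A woman who was absent for weeks and one who was only less productive can both tick the highest category. On the healthcare side, one visit years ago and twelve visits this year give the same answer to question 39.

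Any euro figure published as the cost of UI would in fact be hygiene-product spend alone. The productivity and healthcare parts, which Table 1 justifies by their economic burden, would have no monetary counterpart.

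**Working it through.** **1. The protocol's own count.** Section 9.1.1 says "A total of 29 questions will attempt to acquire information about some of the previously defined variables". Its breakdown is 23 predictor items (n. 1-23), 1 on onset (n. 35), 1 on sexuality (n. 36) and 4 on costs (n. 37-40): 23 + 1 + 1 + 4 = 29. The count is reproduced, and 4 of the 29 items carry the costs domain.

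**2. Each cost item set against what a cost needs** (appendix, questions 37-40).

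| Item | Table 1 row | Count? | Amount? | Period? |
|---|---|---|---|---|
| 37 | Work productivity | No | No | None stated |
| 38 | Hygiene products | Not needed | Yes, banded euro | Weekly |
| 39 | Healthcare use: visits | No | No | None stated |
| 40 | Healthcare use: treatments | No | No | Current, by its wording |

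- Items with a count or an amount: 1 of 4 (question 38).
- Table 1 cost rows with no quantity: 2 of 3. Counting visits and treatments separately, 3 of 4 variables.
- The four items share no common period.
- In question 39, gynaecologist and urologist share one box, and midwife, nurse and physiotherapist share another. A tariff by profession could not be attached either.

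**3. What question 38 does give.** Annual figure = weekly bound × 52.

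| Band (euro per week) | Euro per year |
|---|---|
| No product bought: 0 | 0 |
| Under 3 | 0 to under 156 |
| Up to 5 (read as 3-5) | 156 to 260 |
| 6 to 10 | 312 to 520 |
| Over 10 | over 520, no upper bound |

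Read literally, the third band is 0-5 (0 to 260 a year) and overlaps the second. Nothing covers the interval between 5 and 6.

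An illustration, assuming equal shares of women in the five bands, band three read as 3-5, and a cap on the top band of 15 or 30 euro:

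- Lower mean = (0 + 0 + 3 + 6 + 10) / 5 = 3.8 euro per week.
- Upper mean, cap 15 = (0 + 3 + 5 + 10 + 15) / 5 = 6.6 euro per week.
- Upper mean, cap 30 = (0 + 3 + 5 + 10 + 30) / 5 = 9.6 euro per week.

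The shares and the caps are assumptions, not protocol figures. They show that product spend per woman is imprecise but estimable. No corresponding calculation can be written for questions 37, 39 or 40, because there is no number to enter.

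**4. Can the gap be closed later?** Under section 8 each woman completes the form on a single occasion, and the data are anonymous. Section 16 adds that the database cannot be attributed to an individual. Section 16.1 mentions an identification number in a register, but the protocol provides for no recontact and no linkage to records. Days lost, visits and treatment spend that are not asked on the form are not obtainable afterwards.

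**The case against.** The strongest reply is that the protocol never promises a monetary total, a cost per woman, unit costs or a costing method. Sections 4 and 5 speak of describing costs and of an association with UI. Every Table 1 cost variable has a matching question, and only the product row is itself labelled as a cost. The other rows are productivity and utilization, which can be reported as proportions: any visit by type of professional, any current treatment, self-rated effect on work. Short categorical items are a defensible choice in a self-completed prevalence survey, and the primary outcome is untouched.

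Much of this stands. A reader might infer that the costs outcome cannot be derived at all, or that no cost per woman is computable. The documents do not support that: question 38 gives a banded weekly product cost per woman, and the other three items can be described. A reader might also take question 39 as a lifetime question. Its wording does not say so: questions 8 and 9 contain the Italian word for *ever* and question 39 does not, so its period is simply unstated.

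The reply does not remove the mismatch. Section 9.1.1 names direct and indirect costs as the subject of all four items, and Table 1 files productivity and utilization under Costs for economic reasons. Proportions describe use of care and perceived work impact, and are not costs. An analysis plan cannot repair this, because the quantities are never collected.

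**Conclusion.** The point holds in a limited form. Product spend per woman can be estimated, in bands. Indirect cost, healthcare cost and total cost per woman cannot, because questions 37, 39 and 40 carry no count or amount, questions 37 and 39 carry no recall period, and question 37 merges absence with reduced productivity. This affects two of the three Table 1 cost rows and three of the four items that section 9.1.1 describes as covering direct and indirect costs.

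The conclusion rests on the form as printed in the appendix and on the data being anonymous and collected once, as sections 8 and 16 state. It concerns one component of the secondary outcomes and does not touch prevalence. It should be corrected before data collection, since it cannot be corrected afterwards.

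**What to change.** Change only the researcher-written items and leave the two validated questionnaires as they are.

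- **Question 37:** split it into (a) the number of working days missed because of leakage over a stated recall period and (b) reduced productivity, keeping the present four-point scale.
- **Question 39:** ask for the number of visits per type of professional over a stated period, with the out-of-pocket amount.
- **Question 40:** ask for out-of-pocket spend on treatment over a stated period.
- State the periods so that each can be converted to one common period alongside the weekly spend of question 38.

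The cost is a few number fields, slight extra burden, some recall error, and a brief re-check of the changed items, which would fall outside the existing pilot of 13 women. Valuing lost days, or visits not paid by the woman, would still need outside unit values. Reduced productivity would remain a rating and not a cost.

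If the form is to stay unchanged, reword sections 4, 5 and 9.1.1. The outcome would then be weekly spend on hygiene products, any specialist visit, any current treatment and self-rated work interference, and the phrase on direct and indirect costs would be dropped. That costs only a change of wording, at the price of giving up any claim to estimate indirect or healthcare cost.

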9.1.3 Incontinence Impact Questionnaire-7 (IIQ-7)

The Incontinence Impact Questionnaire-7 (IIQ-7) was developed in 1994 to assess the impact on life of urinary incontinence among women (Shumaker et al., 1994).

IIQ-7 is a self-administered, seven-item questionnaire referring to the individual's perceived impact of urinary incontinence on daily activities, relationships, and feelings. Each item has a four-point response scale, where individuals rate the extent to which urine leakage affects their daily functioning (0 = not at all;

 I.R.C.C.S. Ospedale San Raffaele	STUDY PROTOCOL	WUIPS Version n. 1 23.08.2023
--	-----------------------	--

1 = slightly; 2 = moderately; 3 = greatly). According to the original authors, this tool examines four domains: physical activity (items 1 and 2), travel (items 3 and 4), social activities (item 5) and emotional health (items 6 and 7). The sum is averaged and the mean (from 0 to 3) is multiplied by 33 1/3 to obtain a score on a 0–100 scale (Uebersax et al., 1995). A higher score indicates more severe symptoms and lower quality of life (Monticone et al., 2020).

Overall, the Italian version of the Incontinence Impact Questionnaire-7 shows acceptable basic psychometric properties: time to complete the questionnaire is almost four minutes, Cronbach's α is 0.88, item-scale correlations are all > 0.66 , and item-rest correlation values (rs) range from 0.53 (item 1 "Household chores") to 0.70 (item 4 "Travel > 30 min away from home"). Test-retest reliability is excellent (ICC 2.1 = 0.92 with 95% confidence interval 0.88–0.94). The Standard Error of Measurement and Minimum Detectable Change₉₅ are, respectively, 6.5 and 18.1 points (Monticone et al., 2021). The entire questionnaire is presented in the Appendix (questions n. 28-34).

10. DATA MANAGEMENT AND QUALITY CONTROL

The data collection process will be carried out by nurses and midwives of the four involved hospitals and Vita-Salute San Raffaele University, who will be specifically trained by the research group. The data of the survey and the questionnaires will be collected in the eCRF. Only researchers and authorized users will be able to view the dataset. It will present suitable privacy and anonymity protection requirements according to the provisions of European law (General Data Protection Regulation (GDPR), 2016; available at: <https://gdpr-info.eu/>). Jamovi 2.3.21 software will be used to conduct the data statistical analyses.

11. NUMBER OF CASES

The population sample cannot be decided accurately in advance. Population studies from numerous countries have reported that the prevalence of UI among all adult women ranged from approximately 5% to 70% worldwide, with most studies reporting a prevalence of UI in the range of 25–45% (Miano et al., 2012; Milsom & Gyhagen, 2019). To date, limited epidemiologic research has been conducted in Italy on this matter. One of the most recent Italian studies was conducted in 2002 and prevalence of UI was found to be 10.2% in a sample of 13365 women older than 40 years (Miano et al., 2012; Parazzini, Lavezzari & Arbitani, 2002).

To define an indicative sample size for our search, reference will be made to the sample considered by two prevalence studies conducted in some specifical Italian districts. The first one proposed telephonic interviews to the population of a big area composed by six cities, including a total of 2.767 women aged ≥ 40 years old (Bortolotti et al., 2000). The second study investigated by questionnaire the prevalence and characteristics of UI in a female sample composed by 2.900 subjects aged between 18 and 49 years living in the urban area of Trieste (Siracusano et al., 2003).

Our study will investigate UI prevalence in middle-aged women (40-65 years old) identified in four hospitals in Northern Italy. The competent Departments were asked for data on the average daily accesses of patients to the hospitals involved and the number of female personnel hired with an age range of 40-65

years. As regards the female personnel between 40 and 65 years old hired at San Raffaele Hospital and San Raffaele Turro Hospital, there are 1.842 employees. The sample will be determined based on the data we will receive from other hospitals.

After this study, we could expand the protocol to include other centers to better evaluate the phenomenon and investigate the prevalence in a larger population.

12. SUBJECT'S POTENTIAL RISKS AND BENEFITS

No subject's potential risks are associated with the study and study procedures.

12.1 Bias risk

The included population could present Recall Bias (Delgado-Rodríguez, 2004) during the survey filling, particularly with the ICIQ-UI SF, because it refers to the last four weeks before the filling. This study could present the Underreporting Bias (Delgado-Rodríguez, 2004) because the survey asks for behaviors that negatively affect the personal and social life. The researchers decided to use a bias risk assessment tool during the drafting of the protocol to ensure the study quality. This tool will also accompany the writing of the paper in the future. It consists of a modification and an upgrade of the existing tool developed initially by Leboeuf-Yde and Lauritsen (Leboeuf-Yde & Lauritsen, 1995; Hoy et al., 2012). The tool is based on the Grades of Recommendation, Assessment, Development and Evaluation (GRADE) and Cochrane approaches (Higgins & Green, 2008; Terracciano et al, 2010).

The tool consists of 10 items addressing four domains of bias plus a summary risk of bias assessment: items 1 to 4 assess the external validity of the study (domains are selection and nonresponse bias), and items 5 to 10 assess the internal validity (items 5 to 9 assess the domain of measurement bias, and item 10 assesses bias related to the analysis) (Hoy et al., 2012). Table 3 illustrates the items of the risk of bias tool.

After completing the reporting of the manuscript (except for the risk of bias assessment), two blinded raters will give their opinion on the quality of the study. Response options for individual items (from 1 to 10) will be "low" or "high" risk of bias (if there will be insufficient information in the report to permit a judgment for a particular item, then the item will be deemed to be at high risk of bias). Response options for the summary assessment (item 11) will be "low", "moderate", or "high" risk of bias (Hoy et al., 2012). Overall interrater agreement will be calculated by considering each of the 10 items plus the summary assessment.

Table 3 - The items of the risk of bias tool

#	Item
1	Was the study's target population a close representation of the national population in relation to relevant variables?
2	Was the sampling frame a true or close representation of the target population?

 I.R.C.C.S. Ospedale San Raffaele	STUDY PROTOCOL	WUIPS Version n. 1 23.08.2023
--	-----------------------	--

3	Was some form of random selection used to select the sample, or was a census undertaken?
4	Was the likelihood of nonresponse bias minimal?
5	Were data collected directly from the subjects (as opposed to a proxy)?
6	Was an acceptable case definition used in the study?
7	Was the study instrument that measured the parameter of interest shown to have validity and reliability?
8	Was the same mode of data collection used for all subjects?
9	Was the length of the shortest prevalence period for the parameter of interest appropriate?
10	Were the numerator(s) and denominator(s) for the parameter of interest appropriate?
11	Summary item on the overall risk of study bias

